Wound Dressing in Patients with Hidradenitis Suppurativa: A Pilot Study

STUDY PROTOCOL
PROTOCOL NUMBER 20191046
NCT04194541

Principal Investigator:
[name]

[name] Department of Dermatology & Cutaneous Surgery, University of Miami Miller School of Medicine.

[contact] or [contact] (24-hour page operator)

Email Address: [contact]

Protocol Version No.3 Date: April 6, 2022

1) Objectives*

The primary purpose of this research is to determine how the types of wound dressings affect quality of life for people with Hidradenitis Suppurativa (HS). The secondary purpose is to evaluate the utility of a starter kit concept for wound care in people with HS.

1. Primary outcome: quality of life as measured by the DLQI instrument.
2. Secondary outcomes include:
 - a. Average pain as measured on NRS
 - b. Maximal pain as measured on NRS
 - c. Sleep assessment as measured on 5-point likert scale
 - d. Drainage assessment as measured on 4-point likert scale
 - e. Odor assessment as measured on 4-point likert scale
 - f. Patients' overall preference of dressings for HS as measured on a 5-point likert scale
 - g. Which dressings work best for which parts of the body as measured by patient log
 - h. Frequency of dressing changes required as measured by patient log
 - i. *HS-Physician's Global Assessment (HS-PGA)*
 - j.

Study Endpoints:

Primary endpoint	Change in DLQI from baseline to week 6
Secondary endpoint	Change in average pain NRS from baseline to week 6
Secondary endpoint	Change in maximal pain NRS from baseline to week 6
Secondary endpoint	Change in sleep rating from baseline to week 6
Secondary endpoint	Change in drainage rating from baseline to week 6
Secondary endpoint	Change in odor rating from baseline to week 6

Secondary endpoint	Overall dressing preference for HS as noted by subjects on patient log
Secondary endpoint	Dressing preference for body parts as noted by subjects on patient log
Secondary endpoint	Average frequency of dressing changes as noted by subjects on patient log
Secondary endpoint	Change in HS-PGA at 6 weeks after initial assessment

2) Background*

Hidradenitis suppurativa (HS) is a chronic, inflammatory, skin condition characterized by recurrent, painful, draining nodules and abscesses, with resultant skin tunneling and scar formation. HS most commonly affects intertriginous areas such as the axillae, groin, buttocks, and breasts or inframammary region.¹ In moderate to severe stages of disease, destruction of the normal skin's architecture leads to the formation of sinus tracts and fistulas with dermal and subcutaneous fibrosis.¹ It is estimated that 1-4% of the population is affected by HS.¹

One of the many challenging aspects that HS patients are faced with on a daily basis is wound care. Many HS abscesses and draining nodules and tunnels require frequent dressing changes, up to multiple times daily, given their high exudative nature.¹ Wound care in HS is further complicated by the anatomical predilection of HS wounds. Many dressings on the market are designed to be placed over flat surfaces, and it is often difficult for HS patients to accommodate these flat dressings over the dynamic contours of intertriginous areas such as the axillae, groin, and buttocks.

It is well known that the need for frequent dressing changes due to the heavy exudate in some patients and its odor, significantly impacts patient's quality of life.¹ However, there currently is no standard wound care protocol in place for addressing the wide variety of lesions seen in HS.² Therefore, we have designed a study where we will provide HS patients with different types, sizes, and quantities of FDA-cleared dressings, and we will ask them to keep a log of which types of dressings they found most useful for their wounds. Average as well as maximal pain scores will be measured on a numeric scale (NRS). Patient satisfaction, ease of use of dressings, and dressing preferences will be measured with a 5-point likert scale. Patients

will also be asked to log their dressing changes in order to track how often dressing changes are needed in HS. HS-PGA, drainage, perceived odor, and quality of sleep will be assessed (Table 1).

We will additionally study how the usage of antimicrobial dressings will have an effect on the wound microbiome in order to see how this affects healing in the setting of HS. The presence of bacteria in the wound bed will be determined by analyzing the collected wound swab samples. Standard molecular techniques will be utilized for bacterial analysis. The purpose of collecting swab samples is purely qualitative in its intent to gather data on bio-bioburden and microbiome composition. Ulcer swab results are not indicated for therapeutic treatment nor diagnosis of infection. The results of sample swabs will not have an impact on the treatment plan for each participant.

3) Inclusion and Exclusion Criteria*

Inclusion criteria:

- Men and women ≥ 18 years of age
- Diagnosed with Hidradenitis Suppurativa (all stages of disease) by Dermatologist
- Presence of at least one lesion with active drainage
- Willing and able to provide informed consent

Exclusion criteria:

- Subjects younger than 18-years-old.
- Prisoners
- Pregnant or lactating women
- Adults unable to consent

4) Procedures Involved*

Study duration:

Each subject will have three visits total over a 6-week period.

Recruitment and procedures:

Participants recruited for this study will be patients at University of Miami Hospital (UMH) outpatient dermatology clinics and wound care centers, who present to UMH with a diagnosis of Hidradenitis Suppurativa (HS). During their office visit, patients will be invited to participate in a six-week study to determine which dressings are best suited for patients with HS.

Potential subjects will be informed of the study during their standard of care appointment and then asked if they would like to participate. After signing informed consent, a physical exam will be performed and information on the subjects' demographics, and medical history will be collected (visit 0). Quality of life will be assessed with DLQI instrument. Maximal and average pain will be assessed on a 5-

point likert scale. Quality of sleep, drainage, and odor will be assessed as well (Table 1). Photographs and measurements will be taken of wounds associated with HS. Any active wounds will receive standard of care, including cleaning and debridement to remove all nonviable soft tissue from the wound by scalpel, tissue nippers and/or curettes when appropriate. Wound swab samples will be collected from patients from one active wound at each visit. This site will be identified during the baseline visit. If debridement is indicated as part of standard care, prior to debridement of the wound, a wound swab sample will be collected from the wound bed. In circumstances where a layer of nonviable tissue is preventing swab collection, the swab sample should be collected during the course of the debridement process wherein the wound bed has been exposed. Subjects will be provided with a kit that will include 3 types of FDA-cleared dressings (1) Cutimed® Sorbact® Hydroactive B, 2) Cutimed® Siltec®, and, 3) Sorbion® Sana multi-star) that are available on the market and general wound care supplies (i.e. tape, gauze) that are also FDA-cleared and available on the market. Dressing instructions involve applying desired dressing daily to affected areas and securing with tape as needed. Participants may change dressings as needed. Instructions will be reviewed with participants upon enrollment. Participating subjects will also be given a 2-week log where they will be instructed to fill in which dressings they used on which wounds, and how often they changed the dressings.

Subjects will receive weekly phone calls in between follow ups (for a total of 4 phone calls) by the research team where they will be asked to answer questions on average and maximal pain, quality of sleep, drainage and odor. Subjects will be asked to follow up in 14 +/- 3 days from visit 0 (visit 1), at which point the physical exam will be performed. Maximal and average pain will again be assessed on a 5-point likert scale. Quality of sleep, drainage, and odor will be assessed as well (Table 1). Photographs and measurements of HS wounds will be taken and the dressing logs will be collected and evaluated. Wound swab samples will be collected from the wound that was pre-identified at baseline visit. Participants will share with study personnel which dressings were most useful to them, and this will dictate the dressing type that each subject receives for the remaining 4 weeks of the study period.

Visit 2 will take place 28 +/- 3 days after visit 1. Subjects will follow up for an end of treatment visit where they will have a physical exam. Maximal and average pain will again be assessed on a 5-point likert scale. Quality of sleep, drainage, and odor will be assessed as well (Table 1). Photographs and measurements of HS wounds will be taken. Wound swab samples will be collected from the wound that was pre-identified at baseline visit. Subjects' medical records will be reviewed to collect medical history, treatment plans and disease progress. Please see Table 1 below detailing the schedule of events.

Finally, in order to correlate the above outcomes with independent disease progression, HS-PGA score will be calculated at visits 0, 1 and 2. The HS-PGA instrument is a 6-point scale used to assess overall disease severity. HS-PGA will

be completed at baseline and follow up visits (Table 1). HS affected areas will be evaluated and given a numerical score based on presence of abscesses, draining fistulas, inflammatory nodules, and non-inflammatory nodules. Then the points are added to create one global score. A 2 point reduction and above is considered a meaningful clinical response.

Assessments:

1. Maximal NRS:

Please rate your pain **at its worse** over the last 24 hours on the scale below.

2. Average NRS:

Please rate your pain **on average** over the last 24 hours on the scale below.

3. Drainage assessment:

How much did your lesion(s) drain during the past 24 hours?

No draining	A little draining	Moderate draining	A lot of draining
1	2	3	4

4. Sleep assessment:

How much was your sleep disturbed by HS last night?

Not at all	A little bit	Moderately	A great deal	Unable to sleep
1	2	3	4	5

5. Odor assessment:

How would you rate the odor caused by the draining of your lesion(s) during the past 24 hours?

No odor	A little odor	Moderate odor	A lot of odor
1	2	3	4

6. Dressing's ease of use assessment:

How easy to use are your current dressings?

Very Difficult	Difficult	Neutral	Easy	Very Easy
1	2	3	4	5

7. Dressing satisfaction:

How satisfied are you with your current dressings?

Strongly Dissatisfied	Dissatisfied	Neutral	Satisfied	Strongly Satisfied
1	2	3	4	5

8. HS-PGA:

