Appendix Table 1. Hidradenitis Suppurativa Physician's Global Assessment Scale

Rating	Description
Clear	0 abscesses, 0 draining fistulas, 0 inflammatory nodules, and 0 noninflammatory nodules
Minimal	0 abscesses, 0 draining fistulas, 0 inflammatory nodules, and presence of noninflammatory nodules
Mild	0 abscesses, 0 draining fistulas, and 1–4 inflammatory nodules or 1 abscess or draining fistula and 0 inflammatory nodules
Moderate	0 abscesses, 0 draining fistulas, and ≥ 5 inflammatory nodules or 1 abscess or draining fistula and ≥ 1 inflammatory nodule or 2–5 abscesses or draining fistulas and < 10 inflammatory nodules
Severe	2–5 abscesses or draining fistulas and ≥ 10 inflammatory nodules
Very severe	> 5 abscesses or draining fistulas

Table 1: Schedule of Events

	Baseline Visit Day 0	Phone call 1 Day 7	Follow-Up Visit Day 14	Phone call 2 Day 21	Phone call 3 Day 28	Phone call 4 Day 35	End of Treatment Visit Up to Day 42 after Baseline Visit
Visit Window		7 +/- 3 Days from Baseline Visit	14 +/- 3 Days from Baseline Visit	7 +/- 3 Days from Follow-Up Visit	14 +/- 3 Days from Follow-Up Visit	21 +/- 3 Days from Follow-Up Visit	28 +/- 3 Days from Follow-Up Visit
Visit #	0		1				2
Informed Consent/PHI authorization	X						
Demographics	X						
Medical History ^A	X						
Concomitant Medications & Procedures Assessment	X		X				X
Physical Exam ^B	X		X				X
Inclusion/Exclusion Determination	X						
Wound(s) Photograph	X		X				X
Dermatology Life Quality Index (DLQI)	X						X
Average 24 hours pain Score (NRS)	X	X	X	X	X	X	X
Maximal 24 hours pain Score (NRS)	X	X	X	X	X	X	X
Review Dressing Logs			X				X
Sleep assessment	X	X	X	X	X	X	X
Drainage assessment	X	X	X	X	X	X	X

Dressing Satisfaction	X		X				X
Dressings' Ease of Use	X		X				X
Odor assessment	X	X	X	X	X	X	X
HS-PGA	X		X				X
Wound Swab Sample Collection	X		X				X
Adverse Events Assessment			X				X

A: Detailed HS history will be gathered, including current wound care regime (types and number of dressings utilized per week, including an estimate of anticipated dressings needed per week), exacerbating and alleviating factors; B: Hurley staging will be assessed, as well as types (inflammatory, sinus tracts, ulcerations), number, and location of lesions

5) Data and Specimen Banking*

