6.2 Dressing Logs and Photographs

The dressing logs and photographs collected from each patient will be de-identified and stored in a computer located in the Dermatology Research office. The computer

is located in a locked room in the University of Miami Hospital West Building, Room 506, [name].

Statistical analysis will be performed using software already available in the lab. This information will be protected in a locked office (see Confidentiality section below) and will only be able to be accessed by the primary investigator and the co-investigators. The photographs will then be downloaded as encrypted, de-identified JPEG/TIFF files and stored in the PI computers protected by login and password (see section 16).

6) **Data Management***

The investigator (or research staff) will record the data collected in a manner that does not include any direct identifiers of the subject. The investigator will assign a code to each subject and link the code to the subject's identity. The link to the subject's identity will be maintained on a document separate from the research data. Both documents will be stored on password-protected media on a University of Miami encrypted device. The data will be stored for at least 3 years after the study has concluded and will be destroyed at the earliest opportunity in accordance with University of Miami's policies thereafter. Data will only be accessed by designated study team members.

Statistical analysis of collected data will be performed using IBM SPSS Statistics for Windows (IBM Corporation, Armonk, NY, USA). Mean and range will be calculated for continuous variables. Pearson's chi-squared test will be used to test for independence between categorical variables; for expected values less than 5, Fisher's exact test of independence will be used.

Adverse Events

7) **Adverse Events***

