Patients will be recruited from outpatient dermatology clinics and wound centers at the University of Miami Clinics and Hospital at [name]. Subjects will be offered follow up at outpatient dermatology research offices located at the University of Miami Hospital West Building, [name]. All of the necessary procedures for the study will take place at this location.

11) Resources Available

[name]., is a dermatologist with expertise in wound healing disorders including Hidradenitis Suppurativa; he will be the primary investigator on this study. All subjects will be recruited from outpatient dermatology clinics and wound centers and he can perform detailed wound and skin evaluations.

All associated study personnel are CITI certified and have extensive data analysis training.

12) Prior Approvals

None.

13) Recruitment Methods

Thirty subjects (30) with a diagnosis of Hidradenitis Suppurativa will be recruited by the Investigator and study staff. Subjects will be recruited from outpatient dermatology clinics and the Wound Care Center at the University of Miami. During their standard visit, subjects will be offered the opportunity to enroll in the study. If subjects agree to take part in this study, study staff will guide subjects through the informed consent process.

Subjects will be asked to sign the informed consent form and the photo consent form before the study procedures begin. Subjects will be given ample time to consider the study and all questions will be answered by study staff. Subjects will be enrolled from the date of protocol approval for a 12 months period.

14) Local Number of Subjects

This is a pilot study for which we intend to reach 20 subjects. We anticipate a high drop-out rate, and therefore intend to recruit and enroll a total of 30 subjects locally.

15) Confidentiality

The camera will be stored in a locked office in [name] until the end of the recruitment. The collected coded and encrypted images will be stored in the computers found at the research office protected by a password. The collected coded dressing logs will be stored at the research office in a locked cabinet. Both the encrypted images and the dressing logs will be securely stored for at least 3 years after the research project has concluded. Please see section 7 ('Data

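### Five secondary scales are rated seven times, but the plan analyses only the baseline-to-week-6 change and has no method for repeated or missing ratings despite expected heavy drop-out

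*Combined protocol and SAP*

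**What the plan says.** Section 1 (Study Endpoints) defines five secondary endpoints as two-point changes: "Change in average pain NRS from baseline to week 6", "Change in maximal pain NRS from baseline to week 6", "Change in sleep rating from baseline to week 6", "Change in drainage rating from baseline to week 6", and the same form for odor.

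The schedule collects far more. Section 4 states: "Subjects will receive weekly phone calls in between follow ups (for a total of 4 phone calls) by the research team". The calls cover all five scales. In Table 1 (Schedule of Events) the row beginning "Average 24 hours pain Score (NRS" is marked in all seven columns, as are the rows for maximal pain, sleep, drainage and odor. The items listed under Assessments in section 4 ask about the previous 24 hours or the previous night.

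The only analysis text is in section 6. For continuous variables it says "Mean and range will be calculated for continuous variables". For categorical variables it names Pearson's chi-squared test, or Fisher's exact test when expected counts are small. It names no analysis population, missing-data rule or repeated-measures method.

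Section 14 sets a target of 20 subjects and continues: "We anticipate a high drop-out rate, and therefore intend to recruit and enroll a total of 30 subjects locally".

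**The concern.** A change to week 6 needs a week-6 value. With no missing-data rule, the analysis falls by default on subjects who have one, although the protocol does not say so. The earlier ratings of everyone else then contribute nothing to the endpoint.

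The study has one arm, so no control group shares the attrition. If subjects who benefit least stop attending, those who remain look better than the enrolled group, and the difference is reported as improvement. The day 7 to day 35 ratings are the information that could show and partly correct this, and the plan gives them no stated role in estimating the endpoint.

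**Working it through.** **1. Ratings (Table 1).** Three visits plus four calls give 7 occasions per scale. The endpoint uses 2, leaving 7 − 2 = 5. Over five scales that is 25 of 35 ratings per subject, or up to 25 × 30 = 750 with full attendance.

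**2. Drop-out (section 14).** No rate is stated. The implied rate is 1 − 20/30 = 33.3%, and 20/(1 − 1/3) = 30 returns the stated enrolment. Because the rate is back-calculated, this shows consistency only. The documents give no timing of drop-out, and no SD, effect size, alpha or power for these scales.

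**3. Precision of the week-6 change.** Assumptions: equal SD at each occasion, results in SD units, covariance treated as known, 20 subjects complete and 10 lost.

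Completers only: SE = √[2(1 − ρ)/20], where ρ is the baseline-to-week-6 correlation. The model SE comes from generalised least squares on all ratings, with the 10 losses spread over the weeks.

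| Covariance | Completer SE | Model SE | Reduction |
|---|---|---|---|
| Compound symmetry, 0.3 | 0.265 | 0.246 | 7% |
| Compound symmetry, 0.7 | 0.173 | 0.163 | 6% |
| AR(1), 0.8 (ρ = 0.8⁶ = 0.262) | 0.272 | 0.247 | 9% |

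If all 10 leave straight after baseline, the model variance is (1 − ρ²)/20 + (1 − ρ)²/30. Its ratio to the completer variance is (1 + ρ)/2 + (1 − ρ)/3. At ρ = 0.8 this is 0.900 + 0.067 = 0.967, so the SE ratio is √0.967 = 0.983, a 2% gain. With no drop-out, the week-6 change itself is not sharpened.

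**4. Mean over weeks 3 to 6 (days 21, 28, 35, 42) against one week-6 rating, same subjects.** Under compound symmetry the variance ratio is (1 + 1/4)/2 = 0.625, and √0.625 = 0.791, a 21% smaller SE. Under AR(1) with correlation 0.4 to 0.9 the reduction is about 16% to 18%.

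**5. Bias.** These are simulations on assumed settings with one-third drop-out.

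- *Loss depends on the last observed change* (logit slope 0.5 to 2.0 per SD, worse subjects leaving; compound symmetry 0.3 to 0.7 or AR(1) 0.8 to 0.9). The completer change is biased by about 0.05 to 0.33 SD towards improvement. A likelihood model on all seven ratings is biased by at most 0.005 SD. A likelihood fit on baseline and week 6 alone keeps about 0.03 to 0.18 SD, so the interim ratings are needed for the full correction.
- *Loss depends on unobserved true status* (true change −1.0, slope SD 2, noise SD 1 to 2). Completers show about −1.55 and the model −1.26 to −1.35. It removes (1.55 − 1.35)/0.55 = 36% to (1.55 − 1.26)/0.55 = 53% of the bias.
- *Loss unrelated to outcome.* Both analyses are unbiased.

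**The case against.** **Scope.** A reader might infer that every endpoint ignores interim data. The documents do not support that. DLQI, the primary, is collected only at baseline and end of treatment. Three endpoints come from the patient log, and HS-PGA is scored at the three visits only. The point covers five secondary scales in a single-arm pilot with no stated hypothesis test.

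**Wasted data.** A reader might also infer that the interim ratings cannot be used at all. Section 6 does not confine mean and range to week 6, so a table by time point is permitted. That stands, but such a table does not use a drop-out's earlier ratings in estimating the week-6 change.

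**Size.** Averaging all six post-baseline ratings would cut the SE by 24% under compound symmetry (√[(1 + 1/6)/2] = 0.764) and 31% under AR(1) 0.8. It is tempting to claim that gain. However, that average mixes the three-dressing phase before Visit 1 with the selected-dressing phase after it, and it is not the week-6 endpoint.

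**Bias.** It is tempting to say that the planned analysis will overstate improvement and that a model cures it. The documents say nothing about why or when subjects leave. The cure is complete only if loss depends on observed ratings, and one-day ratings may track true status poorly.

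**Scales.** Section 1, the Background, the Assessments list and Table 1 call pain an NRS, while the visit descriptions in section 4 call it a 5-point Likert scale. No readable text gives the NRS range, so a bias in raw pain points cannot be stated. Drainage and odor have 4 levels and sleep has 5, so a linear model is an approximation. Ratings by phone and in clinic may also differ.

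**Conclusion.** The point holds for average pain, maximal pain, sleep, drainage and odor. The gap is one of analysis: repeated ratings are scheduled and heavy drop-out is expected, but no stated method connects the two.

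The gain for the week-6 estimate is modest, about 6% to 9% in SE under staggered loss and as little as 2% under immediate loss. It would be somewhat less certain once the covariance is estimated from 30 subjects. The stronger reason for the change is protection against selective drop-out, whose benefit ranges from nil to complete depending on a mechanism that the documents do not describe. All correlations and drop-out models above are assumptions, and the one-third rate is implied by 30 and 20 rather than stated. Any drop-out bias in the primary DLQI endpoint is untouched.

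**What to change.** First reconcile the two descriptions of the pain scale. Then add to section 6, for these five scales only:

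- Population: all enrolled subjects with a baseline rating, using every available rating.
- Main estimate: the week-6 change with a 95% CI from a repeated-measures model (SPSS MIXED) with all seven occasions as outcomes, time as a category and a parsimonious covariance structure suited to 30 subjects.
- Beside it: the observed change in subjects who have both ratings, with their number, so that any divergence is visible.
- Sensitivity: an ordinal analysis for the 4- and 5-point items.
- Supportive summary: the mean change from baseline over weeks 3 to 6, labelled as a different quantity from the week-6 change and as a mix of three phone ratings and one clinic rating.
- A sentence stating that the model assumes drop-out is explained by observed ratings, and that it does not extend to DLQI.

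The week-6 endpoints stay as defined. The cost is protocol wording and a little more analysis work, with no new data, visits or software. The downside is reliance on the missing-at-random assumption.
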